- If an empty room is not available, participants will be asked to fill out questionnaires electronically at home

Informed consent will be conducted in-person by the PI. The clinical research coordinator will obtain signatures on the informed consent form and Bill of Rights from the PI and the participant. The participants will be given a copy of the signed forms. Questionnaires will be administered electronically via a link generated from REDCap preferably during the study visit.

Data Management:

All study data will be kept in a secure online REDCAP database. Paper forms, such as study consents, will be kept in a locked file cabinet in a locked office in a secure building.

- **Data Management Procedures:**

- o The data will be entered into a REDCap database. The study team will be responsible for data processing, in accordance with procedural documentation. Database lock will occur once data collection and quality assurance procedures have been completed.

All procedures for the handling and analysis of data will be conducted using good computing practices meeting FDA guidelines for the handling and analysis of data for clinical trials.

Informed Consent:

Informed consent will be obtained in accordance with the Declaration of Helsinki, ICH GCP, US Code of Federal Regulations for Protection of Human Subjects (21 CFR 50.25[a,b], CFR 50.27, and CFR Part 56, Subpart A), the Health Insurance Portability and Accountability Act (HIPAA, if applicable), and local regulations.

The Investigator will prepare the informed consent form, assent and HIPAA authorization and provide the documents to the Sponsor or designee for approval prior to submission to the IRB. The consent form generated by the Investigator must be acceptable to the Sponsor and be

approved by the IRB. The written consent document will embody the elements of informed consent as described in the International Conference on Harmonisation and will also comply with local regulations. The Investigator will send an IRB approved copy of the Informed Consent Form to the Sponsor (or designee) for the study file.

A properly executed, written, informed consent will be obtained from each subject prior to entering the subject into the trial. Information should be given in both oral and written form and subjects must be given ample opportunity to inquire about details of the study. A copy of the signed consent form will be given to the subject and the original will be maintained with the subject's records. Please refer to the section "COVID-19 Protocol Amendments" for an updated consent process.

Data Safety Monitoring Plan:

The Data Safety Monitoring Plan will be implemented by the PI and all key study personnel. The purpose will be to review data relating to safety and efficacy, to conduct and review interim analyses, and to ensure the continued scientific validity and merit of the study, according to the UCSF Data Safety Monitoring requirements. There will be 1 interim review(s) conducted by the PI for the purpose of monitoring study conduct and assessing patient safety. This will include a review of adverse effects, breaches of confidentiality, and unanticipated problems involving risk to participants and others. If there are any serious adverse effects, they will be reported to the IRB in an ongoing fashion. This study will also involve a DSMB, which will be formed by 3 members: a neurologist, an otolaryngologist, and a statistician. They will review any serious adverse events within 5 days and perform 1 interval analysis once half of the target recruitment is achieved.

f. Adverse Events:

An adverse event (AE) is any untoward medical occurrence in a clinical investigation of a patient administered a pharmaceutical product and that does not necessarily have a causal relationship with the treatment. An AE is therefore any unfavorable and unintended sign (including an abnormal laboratory finding), symptom or disease temporally associated with the administration of an investigational product, whether or not related to that investigational product. An unexpected AE is one of a type not identified in nature, severity, or frequency in the current Investigator's Brochure or of greater severity or frequency than expected based on the information in the Investigator's Brochure.

The Investigator will probe, via discussion with the subject, for the occurrence of AEs during each subject visit and record the information in the site's source documents. Adverse events will be recorded in the patient CRF. Adverse events will be described by duration (start and stop dates and times), severity, outcome, treatment and relation to study drug, or if unrelated, the cause.

g. Serious Adverse Experiences (SAE):

SAE is defined as any AE occurring at any dose that results in any of the following outcomes:

- Death

- A life-threatening adverse experience
- inpatient hospitalization or prolongation of existing hospitalization
- A persistent or significant disability/incapacity
- A congenital anomaly/birth defect
- Other important medical events may also be considered an SAE when, based on appropriate medical judgment, they jeopardize the subject or require intervention to prevent one of the outcomes listed

Serious Adverse Experience Reporting:

Study sites will document all SAEs that occur (whether or not related to study drug) per UCSF CHR Guidelines. The collection period for all SAEs will begin after informed consent is obtained and end after procedures for the final study visit have been completed. In accordance with the standard operating procedures and policies of the local Institutional Review Board (IRB), the site investigator will report SAEs to the IRB.

Privacy Protection:

The study will be conducted according to the Declaration of Helsinki, Protection of Human Volunteers (21 CFR 50), Institutional Review Boards (21 CFR 56), and Obligations of Clinical Investigators (21 CFR 312).

Clinical information will not be released without written permission of the subject, except as necessary for monitoring by the FDA. The Investigator must also comply with all applicable privacy regulations (e.g., Health Insurance Portability and Accountability Act of 1996, EU Data Protection Directive 95/46/EC).

Protocol Amendments:

Any amendment to the protocol will be written by the PI. Protocol amendments cannot be implemented without prior written IRB approval except as necessary to eliminate immediate safety hazards to patients. A protocol amendment intended to eliminate an apparent immediate hazard to patients may be implemented immediately, provided the IRBs are notified within five working days.

IRB:

The protocol and consent form will be reviewed and approved by the UCSF IRB prior to study initiation. Serious adverse experiences regardless of causality will be reported to the IRB in accordance with the standard operating procedures and policies of the IRB, and the Investigator will keep the IRB informed as to the progress of the study. The Investigator will obtain assurance of IRB compliance with regulations.

Data Analysis Plan:

Subjects will be divided by study status into several groups.

1. Per Protocol Analysis
 - a. Signed Consent
 - b. 4 study visits (in person or virtual) within:
 - i. SV2 (day 30) no earlier than day 23, and no later than day 44.
 - ii. SV3 (day 60/day 30 after SV2) no earlier than day 23 after SV2, and no later than day 37 after SV2.
 - iii. SV4 (day 120/day 60 after SV3) no earlier than day 50 after SV3, and no later than day 70 after SV3.
 - c. Received same drug (galcanezumab or placebo) for all doses during the trial
 - d. Completed Day 90 injection within 7 days of target date, so 23 to 37 days after SV3
 - e. 80% or better adherence to text message
 - f. Filled out all questionnaires
2. Intent to Treat
 - a. Everyone who signed consent and got at least one dose of study drug who does not meet per protocol criteria
3. SV2 failure
 - a. Signed consent but did not meet eligibility during the baseline month (less than 80% adherence to texting, or fewer than 4 definitive dizzy days or SV2 VM-PATHI less than 25)
4. SV1 failure
 - a. Signed consent but then VM-PATHI score too low on SV1
5. Screen failure
 - a. Did not meet inclusion/Exclusion so did not sign consent

Responsibilities of Study Team Members:

[name] (Principal Investigator): [name] is an Assistant Professor in the Department of Otolaryngology – Head and Neck Surgery, and the director of the Balance and Falls Center at UCSF. [name] will serve as PI for this project, and will supervise experimental design, data analysis, and summarizing the result for public disclosures to the academic community.

[name]: Co-investigator: [name] is an Assistant Professor of Neurology, and a member of the UCSF Headache Center. She will assist will all aspects of the study.

[name]: [name] is the director of the Headache Center at UCSF, and will assist in all aspects of the study.

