To assess the response rate of subjects to galcanezumab in vestibular migraine, as measured by a 100%, 75%, 50%, and 25% reduction in definitive dizzy days, comparing baseline data (month 0 to 1), to after treatment data (months 3-4), comparing between active treatment and placebo arms.

To assess the time course of response to galcanezumab in vestibular migraine, measured by definitive dizzy days per month, comparing active treatment and placebo arms, from months 0 to 4.

To assess the efficacy of galcanezumab in treating vestibular migraine, as assessed by DHI (Dizziness Handicap Inventory) score change between baseline (month 0) and after three months of treatment (month 4), comparing active treatment and placebo arms.

To assess the efficacy of galcanezumab in treating quality of life in vestibular migraine, comparing the change in baseline PROMIS SF v1.2- Global Health scores to scores after 3 months of treatment (at month 4), across active treatment and placebo arms.

Study Endpoints:

Primary:

VM-PATHI (Vestibular Migraine Patient Assessment Tool and Handicap Inventory) score.

Secondary:

Definitive dizzy days, measured with a daily text message, with any day where dizziness is rated as a 2 (moderate) or higher counting as a definitive dizzy day.

Response rates, as measured by percentage of subjects in each arm experiencing a 100%, 75%, 50%, 25%, 0% reduction in definitive dizzy days.

Dizziness Handicap Inventory
PROMIS SF v1.2- Global Health

Statistical Methods:

Primary Endpoint:

VM-PATHI score changes between baseline and after treatment (month 4) will be compared between active treatment and placebo arms using a paired two-tailed t-test.

Secondary Endpoint:

Definitive dizzy days/month, comparing baseline to after treatment, between active treatment and control arms, will be assessed using a paired two-tailed t-test.

Response rates will be reported per category (100%, 75%, 50%, 25%, and 0%) for both active treatment and control arms. Number of subjects who experience 50% or better reduction in dizziness days will be compared using chi squared test.

Dizziness Handicap Inventory will be compared between active treatment and control arms, looking at change in score from baseline to month 4, using a paired two-tailed t-test.

PROMIS scores, comparing subdomain score changes from before (month 0) and after (month 4) treatment, across active and placebo arms, using paired t-test

Subject Selection:

Inclusion criteria:

- Adult age 18 to 75

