These inclusion/exclusion criteria were chosen so that the study has as much real world applicability as possible, while also minimizing risks to subjects. Based on our preliminary data, we believe that with these inclusion and exclusion criteria, and accounting for subjects who don't want to participate and also dropout, we will still be able to recruit enough subjects to meet our recruitment goals within 2 years.

Sample Size:

We have specifically designed this as a pilot study due to lack of data to help inform sample size calculations. However, hypothesizing a difference between VM-PATHI scores between groups of 7 points, and using the standard deviation from the validation of the instrument, we with 50 subjects total, or 25 per arm, we will have 90% power to detect a significant difference at the 0.05 level between groups to assess the efficacy of galcanezumab for vestibular migraine. If we assume a 10% dropout rate in the trial we will still have greater than 80% power to detect a difference.

Clinical Sites:

We will perform this study as a single center. We will be recruiting subjects from both the Otolaryngology-Head and Neck Surgery and Neurology departments. In a previous study where we developed the VM-PATHI, we were able to recruit around 80 subjects with vestibular migraine in a little over 1 year.

Study Visit Timeline:

The study visits will be scheduled within +/- 4 days of the expected timeline. This flexibility is based on the clinic availability dates of the PI and other providers.

- Study Visit 1 (SV1) = Day 0 / Month 0
- Study Visit 2 (SV2) = Day 30 / Month 1
- Study Visit 3 (SV3) = Day 60 / Month 2
- Study Visit 4 (SV4) = Day 120 / Month 4

Re-Enrollment Policy:

For participants who met all inclusion criteria AND none of the exclusion criteria (except for not having the minimum required VM-PATHI score and/or definitive dizzy days), they can re-enroll in the study at a later date when they feel their symptoms are worse. At that time, the participant would have to start over from Day 0 and undergo screening again.

Randomization:

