- Early Discontinuation of Study Drug:**

- o A subject may be discontinued from study treatment at any time if the subject, the investigator, or the Sponsor feels that it is not in the subject’s best interest

to continue. The following is a list of possible reasons for study treatment discontinuation:

- Subject withdrawal of consent (or assent)
- Subject is not compliant with study procedures
- Adverse event that in the opinion of the investigator would be in the best interest of the subject to discontinue study treatment
- Protocol violation requiring discontinuation of study treatment
- Lost to follow-up
- Sponsor request for early termination of study
- Positive pregnancy test (females)

If a subject is withdrawn from treatment due to an adverse event, the subject will be followed and treated by the Investigator until the abnormal parameter or symptom has resolved or stabilized. All subjects who discontinue study treatment should come in for an early discontinuation visit as soon as possible and then should be encouraged to complete all remaining scheduled visits and procedures. All subjects are free to withdraw from participation at any time, for any reason, specified or unspecified, and without prejudice. Reasonable attempts will be made by the investigator to provide a reason for subject withdrawals. The reason for the subject's withdrawal from the study will be specified in the subject's source documents.

c. Analysis of Primary Endpoint:

d. For the primary endpoint, which is the change in VM-PATHI scores between month 1 and month 4 as compared between the galcanezumab arm and the placebo arm, a paired two-tailed Student's t-test will be used, provided the data is normally distributed. This will be conducted with an intent-to-treat analysis. Significance will be set at alpha of 0.05.

e. Analysis of Secondary Endpoints:

Definitive dizzy days/month, comparing baseline (month 0 to 1) to after treatment (month 3-4), between active treatment and control arms, will be assessed using a two-tailed t-test.

Response rates will be reported per category (100%, 75%, 50%, 25%, and 0% reduction in definitive dizziness days, comparing month 0 to 1 to month 3 to 4) for both active treatment and control arms. Number of subjects who experience 50% of better reduction in dizziness days will be compared using Chi Squared test.

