Dizziness Handicap Inventory will be compared between active treatment and control arms, looking at change in score from baseline to month 4, using a two-tailed t test.

PROMIS scores comparing active and placebo arm score changes from before (month 0) and after (month 4) treatment using a paired t-test.

Safety and tolerability data will be summarized by treatment group.

Adverse event rates will be coded by body system and MedDra classification term. Adverse events will be tabulated by treatment group and will include the number of patients for whom the event occurred, the rate of occurrence, and the severity and relationship to study drug.

Initially data will be summarized overall, by patient, and by treatment and control groups. Plots of each outcomes will be displayed graphically over longitudinal time points. Univariate summaries of all variables overall, by patient, and by subgroup will include means and standard deviations for continuous variables and counts and percentages for categorical variables.

Bias:

Bias will be minimized by using a double-blinded study design, with allocation concealment. This will limit selection, performance, and detection bias. In addition, this will help control for potential confounding variables. In addition, by including a placebo control group, we will minimize regression to the mean bias. Finally, by collecting information prospectively, we will minimize reporting bias.

Missing Data:

We will minimize missing data by having the clinical trial coordinator present to help the study subject fill out all data. We anticipate a 15-20% loss to follow up, and have accounted for that in our sample size calculations. Outliers and non-compliant subjects will be included in the analysis. We will perform an intent-to-treat analysis.

Trial Duration:

We estimate that this trial will take approximately 2 years to complete, once subject recruitment is able to begin. That includes 1.5 years for subject recruitment and data collection, and 6 months for closeout and data analysis. If recruitment is slower than expected, we will plan on keeping the trial open for a longer period of time. This seems unlikely based on our prior experience with recruitment in this patient population.

Pharmacy/Study Drug:

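### The primary test is called 'paired', but the two randomised arms contain no pairs, so as written the primary p-value is not uniquely defined

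*Combined protocol and SAP*

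**What the plan says.** Both places that define the primary test call it paired. The opening Statistical Methods section says that VM-PATHI score changes "will be compared between active treatment and placebo arms using a paired two-tailed t-test". The Analysis of Primary Endpoint section describes the change "as compared between the galcanezumab arm and the placebo arm, a paired two-tailed" Student's t-test, conditional on normality, by intent to treat, at alpha 0.05.

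The secondary endpoints are not labelled consistently:

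| Endpoint | Statistical Methods | Later analysis sections |
|---|---|---|
| VM-PATHI (primary) | paired | paired |
| Definitive dizzy days | paired: "between active treatment and control arms, will be assessed using a paired two-tailed t-test" | not paired: "between active treatment and control arms, will be assessed using a two-tailed t-test" |
| DHI | paired | not paired: "looking at change in score from baseline to month 4, using a two-tailed t test" |
| PROMIS | paired | paired: "score changes from before (month 0) and after (month 4) treatment using a paired t-test" |

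The Study Design and Randomization sections describe 1:1 allocation in blocks of 10, stratified by sex and by definite or probable diagnosis. Each subject stays on one treatment. The Sample Size section claims "90% power to detect a significant difference at the 0.05 level between groups" with 25 per arm. The Missing Data section expects 15-20% loss to follow-up and adds "Outliers and non-compliant subjects will be included in the analysis".

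**The concern.** A paired t-test needs a rule that ties each observation in one arm to one observation in the other. This design supplies none. Blocks of 10 and four strata are not pairs, and the only natural pairing, a subject's own baseline and follow-up, is already used when the change score is formed.

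The text leaves three readings open:

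1. A paired test across arms, which needs an invented matching of unrelated subjects.
2. A within-arm paired test of baseline against follow-up, done in each arm. This does not compare drug with placebo.
3. An independent t-test on change scores, with 'paired' used loosely to mean change from baseline.

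Only the third answers the trial's question with a single p-value, and nowhere is it named for the primary endpoint. At stake is whether the primary result is fixed before the data are seen. On the first reading, a second problem follows: a subject with no partner in the other arm must be dropped, which conflicts with the intent-to-treat commitment.

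**Working it through.** **Inputs.** 25 per arm, a 7-point difference and 90% power (Sample Size); two-tailed alpha 0.05 (Analysis of Primary Endpoint); 15-20% loss (Missing Data). The SD is described only as coming from the instrument's validation and no figure is given, so the 90% cannot be reproduced. I solved for the SD that it implies and took 10 and 15 as assumed alternatives.

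**Implied SD.** For an independent t-test the noncentrality is 7 / (SD × √(2/25)), with 48 df and critical t 2.011. Power of 90% requires SD = 7.48, since 7 / (7.48 × 0.2828) = 3.31.

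**Power if a pairing is fixed in advance.** With unrelated subjects the noncentrality is unchanged, but df fall to 24 and the critical t rises to 2.064.

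| SD | Independent (48 df) | Paired (24 df) | Tests on opposite sides of 0.05, 7-point effect |
|---|---|---|---|
| 7.48 (implied) | 90.0% | 88.8% | 3.2% |
| 10 (assumed) | 67.9% | 66.1% | 6.1% |
| 15 (assumed) | 36.6% | 35.4% | 6.1% |

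In 200,000 simulated normal trials with no effect, type I error was 0.050 for both tests, and they disagreed in 1.8% of trials.

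**Dependence on the pairing.** With equal SDs in the two arms, t(paired) = t(independent) / √(1 − r), where r is the correlation that the chosen pairing happens to create. Over random pairings of 25, r has SD 1/√24 = 0.204, so about 95% lie within ±0.40. Starting from an independent p of 0.050 (t = 2.011):

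- r = +0.40: t = 2.011/√0.6 = 2.60, and p is about 0.016 on 24 df.
- r = −0.40: t = 2.011/√1.4 = 1.70, and p is about 0.102.

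Simulation agrees (20 data sets, 10,000 pairings each):

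| Independent p | Central 95% of paired p | Share of pairings below 0.05 |
|---|---|---|
| 0.03 | 0.009 to 0.070 | 80% |
| 0.05 | 0.017 to 0.101 | 40% |
| 0.08 | 0.032 to 0.141 | 11% |

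**If the pairing were chosen after seeing the data.** Taking the smallest p of 2, 5, 10 or 20 random pairings (40,000 null trials) gives type I error of 6.4%, 8.0%, 9.5% or 11.0%.

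**Unmatched subjects.** Completers per arm are taken as independent binomials, Bin(25, 0.85) or Bin(25, 0.80):

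| Loss | P(arms unequal) | Mean number unmatched | P(3 or more unmatched) |
|---|---|---|---|
| 15% | 84% | 2.0 | 32% |
| 20% | 86% | 2.2 | 37% |

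**Within-arm reading.** Suppose both arms improve by 5 points with no drug effect (an assumed figure) and the change SD is 7.48. The noncentrality is 5 / (7.48/√25) = 3.34 on 24 df, so a within-arm paired test is significant about 89% of the time. The background section itself warns of regression to the mean in this population.

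**The case against.** The strongest reply is that nobody would pair strangers across arms. The objectives, the power statement and both primary-analysis passages describe a drug-versus-placebo contrast, and dizzy days and DHI get a plain t-test in the later sections. On that view 'paired' is shorthand for a within-subject change score, the p-value is unique, and this is a labelling slip. Intent is indeed fairly clear. But the later analysis text drops 'paired' for two endpoints and keeps it for the primary, so a reader could take the difference as deliberate, and no section says otherwise.

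Other parts of the reply also stand:

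- Even read literally, the cost is small if the pairing is fixed in advance. With equal arms, the estimated mean difference does not depend on the pairing at all.
- The inflated error rates need someone to search over pairings. Nothing suggests that this is planned, and keeping the allocation file secret until analysis is complete makes it harder, though coded arm labels would not rule it out.
- An independent t-test would also omit subjects with no month 4 score, because no imputation method is given. Pairing adds only about two further exclusions.
- Removing 'paired' does not settle whether the primary baseline is month 0 (Study Objectives) or month 1 (Analysis of Primary Endpoint), or what replaces the t-test if normality fails. Those are separate points.

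None of this makes the named test right for the design.

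**Conclusion.** The concern holds. The named primary test does not fit two independent arms, the error appears in both places that define it, and the secondary endpoints contradict each other on the same word. Read literally, a result at p = 0.050 on the independent test could reasonably be reported anywhere from about 0.017 to 0.101, depending on an arbitrary choice. There is no built-in inflation of type I error, and the power loss is 1.2 to 1.8 points across the SDs examined.

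These figures assume normal change scores with equal SDs and 25 per arm. The power figures also depend on the SD, which the plan does not state. The completer figures assume that loss is independent between subjects and equal in the two arms. Although the trial is a pilot, it sets a formal 0.05 test and claims power for it. The wording must therefore be corrected before the data are analysed.

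**What to change.** Delete 'paired' for VM-PATHI, definitive dizzy days, DHI and PROMIS in Statistical Methods, for VM-PATHI in Analysis of Primary Endpoint, and for PROMIS in Analysis of Secondary Endpoints. The later entries for dizzy days and DHI already omit it.

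For all four endpoints, state: 'Change from baseline will be compared between arms with an independent two-sample two-tailed t-test, reporting the difference in mean change with a 95% confidence interval.' With 25 per arm this has 48 df.

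The cost is a protocol wording change only, with no new data or patients. The sample size stays as it is, because the power statement is already framed as a difference between groups.
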